2. Clinical Specimens

Clinical specimens will be tested with the Alinity s blood screening assay, corresponding comparator method, and supplemental testing assays as needed to determine final status.

a. Study Design

Confidential Information

This material is the property of Abbott Laboratories and must not be disclosed or used, except as authorized in writing by Abbott Laboratories.

Percent agreement will be calculated between Alinity s blood screening assay results and corresponding comparator method results. Supplemental testing will be performed to determine specimen final status. The sensitivity and specificity will be calculated based on specimen final status. For each Alinity s and comparator assay, the specificity will be calculated using results from donor specimens, a presumed zero prevalence population and the sensitivity will be calculated using results from preselected positive populations and from endemic or increased risk populations.

b. Analysis Variables

- Alinity s blood screening assay interpretation and PRISM comparator assay interpretation
- Specimen Category
- Specimen final status according to Supplemental Testing algorithm.

c. Statistical Analysis Method

Percent Agreement

Percent agreement of Alinity s blood screening assay final results and comparator assay final results will be calculated.

Alinity s Assay	Comparator Assay	
	Repeatedly Reactive	Nonreactive
Repeatedly Reactive	A	B
Nonreactive	C	D

$$\text{Percent Agreement} = (A + D) / (A + B + C + D) \times 100\%$$

Initial Reactive Rate and Repeat Reactive Rate

The number and percentage of Alinity s blood screening Assay initially reactive donors, the number and percentage of Alinity s blood screening assay repeatedly reactive donors, and the number and percentage of repeatedly reactive donors that are positive by supplemental testing will be summarized.

Two-sided 95% confidence intervals will be calculated for initial and repeat reactive rates using the exact method based on the binomial distributions.

IR Rate not Reactive on Retest and RR Rate not Positive by Supplemental testing

Confidential Information

This material is the property of Abbott Laboratories and must not be disclosed or used, except as authorized in writing by Abbott Laboratories.

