The number and percentage of Alinity s blood screening assay initially reactive donors that are not reactive on retest and the number and percentage of repeatedly reactive donors that are not positive by supplemental testing will be summarized.

Two-sided 95% confidence intervals will be calculated for IR Rate not Reactive on Retest and RR Rate not Positive by supplemental testing using the exact method based on the binomial distributions.

The following table will be used to calculate assay specificity and sensitivity based on the specimen final status.

Alinity s assay	Final Status		
	Positive	Indeterminate (if applicable)	Negative
Repeatedly Reactive	A	B	C
Nonreactive	D	E	F

Specificity

The calculation of specificity will include results from whole blood donors and plasmapheresis donors. Analyses described in this section will be performed for the combined donors, by specimen type, and by site.

The specificity is calculated as the proportion of nonreactive (NR) specimens from specimens with negative status:

$$\text{Specificity} = F / (C + F) \times 100\%$$

Specificity can be also calculated as the proportion of nonreactive (NR) specimens with negative status from specimens with negative status and repeatedly reactive (RR) specimens with indeterminate status:

$$\text{Specificity} = F / (C + B + F) \times 100\%$$

Two-sided 95% confidence intervals will be calculated for specificity using the exact method based on the binomial distributions.

For the combined donors and by specimen type, the specificity will be calculated for the comparator assay.

Confidential Information

This material is the property of Abbott Laboratories and must not be disclosed or used, except as authorized in writing by Abbott Laboratories.

Histograms

Population distributions for the donor specimens will be presented in histograms and will include mean S/CO values of the nonreactive population, the SD of the population, and the number of SDs from the mean to the cutoff. These histograms will be presented for the combined donor population by site, and by sample type.

Sensitivity

The evaluation of sensitivity will include results of the following specimens: preselected positive, individuals at increased risk of infection, and/or individuals from an endemic area at increased risk of infection.

Sensitivity is calculated as the proportion of repeatedly reactive (RR) specimens from specimens with positive final status:

$$\text{Sensitivity} = A / (A + D) \times 100\%$$

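### Do infected donors whom the Alinity assay misses drop out of the planned analysis?

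*Combined protocol and SAP*

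**What the plan says.** Section IX.B.2.a divides the work by population. For donors, "the specificity will be calculated using results from donor specimens, a presumed zero prevalence population". For the other specimens, "the sensitivity will be calculated using results from preselected positive populations and from endemic or increased risk populations". The Sensitivity paragraph of IX.B.2.c agrees: "The evaluation of sensitivity will include results of the following specimens: preselected positive, individuals at increased risk of infection", to which it adds specimens from endemic areas. Donors are not named there.

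The final-status table in IX.B.2.c crosses the Alinity result (repeatedly reactive or nonreactive) with final status (positive, indeterminate, negative). Its cells are A, B, C in the reactive row and D, E, F in the nonreactive row. On its use the plan says: "The following table will be used to calculate assay specificity and sensitivity based on the specimen final status". Specificity is F/(C+F), or alternatively F/(C+B+F). Sensitivity is A/(A+D), or alternatively A/(A+D+E).

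Two donor summaries use supplemental results. One states that "the number and percentage of repeatedly reactive donors that are positive by supplemental testing will be summarized" and the other that "the number and percentage of repeatedly reactive donors that are not positive by supplemental testing will be summarized". For PRISM, "For the combined donors and by specimen type, the specificity will be calculated for the comparator assay". On S/CO values, "Population distributions for the donor specimens will be presented in histograms".

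Three other sections bear on the point:
- **III.E** sends a donor specimen to supplemental testing if it is repeatedly reactive on either assay or repeatedly gray zone on Alinity. It also supplies HIV, HBV and HCV NAT results for donor specimens.
- **III.F** seeks follow-up for donors whose Alinity result disagrees with final status. It removes seroconverters' index results from specificity.
- **IX.A** requires a listing of all observations, a listing of exclusions with reasons, and an account of how each result was used.

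**The concern.** The objective in section II is performance in donor screening, compared with licensed assays. The most serious error in that setting is an infected donation that the test passes. The plan expects a few such donors to surface: a PRISM repeatedly reactive or Alinity gray zone specimen goes to supplemental testing and may prove positive. Yet such a donor lowers neither Alinity sensitivity, which excludes donors, nor Alinity specificity, whose formulas contain no D. Both supplemental-status summaries start from an Alinity repeatedly reactive result, so they cover only A and B+C. PRISM is treated the same way: an infected donor it misses lowers no PRISM accuracy measure. If this were a true omission, a report could show excellent specificity and high sensitivity in selected specimens and say nothing about missed donors.

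**Working it through.** The plan states no figure for this point, so there is none to reproduce. The check has three parts.

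**1. Where a cell D donor goes under the plan**

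| Output | Does it include donor cell D? |
|---|---|
| Sensitivity, both formulas | No; donors are not in the population |
| Specificity, both formulas | No; only F, C and B appear |
| Repeatedly reactive donors, positive or not positive | No; these are A and B+C |
| Percent agreement with PRISM | Yes; as a disagreement if PRISM is repeatedly reactive, but not split by final status |
| Reactive rates, histograms | Yes, without reference to final status |
| Follow-up (III.F) | Yes; the Alinity result disagrees with final status |
| Listing and usage account (IX.A) | Yes, line by line |
| Final-status table (IX.B.2.c) | It has the cell; the text does not say the table is printed for donors |

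Section IX.B.2.b names both assay interpretations, specimen category and final status as analysis variables. These are all that is needed to fill the table for donors.

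**2. What the planned outputs would show**

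All counts here are assumptions: 15,000 donors, 10 infected and repeatedly reactive on both assays, 13 Alinity-only false reactives, and 2 PRISM-only repeat reactives. Agreement is (10 + 14,975)/15,000 = 99.900%. The Alinity repeat reactive rate is 23/15,000 = 0.153%. The status of the last 2 donors is then varied.

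| The 2 donors are | Alinity F/(C+F) | PRISM F/(C+F) | Donors outside the denominator, less the 10 | True D |
|---|---|---|---|---|
| negative | 14,977/14,990 = 99.913% | 14,988/14,990 = 99.987% | 15,000 − 14,990 − 10 = 0 | 0 |
| infected | 14,975/14,988 = 99.913% | 14,988/14,988 = 100% | 15,000 − 14,988 − 10 = 2 | 2 |
| indeterminate | 14,975/14,988 = 99.913% | 14,988/14,988 = 100% | 15,000 − 14,988 − 10 = 2 | 0 |

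The exact 95% interval for Alinity specificity is 99.852% to 99.954% in every row. Subtraction recovers D in the first two rows. In the third it mistakes indeterminates for missed infections. There the alternative PRISM formula gives 14,988/14,990 = 99.987% and separates the last two rows, and the listing settles the matter in any case.

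Seroconverters removed under III.F are mostly a different matter. Follow-up starts from an Alinity result that disagrees with final status, so a removed index result with negative status would ordinarily have been Alinity repeatedly reactive: an early detection, not a miss. Suppose 2 of the 13 Alinity-only reactives seroconvert and the 2 PRISM-only reactives are negative. The denominator is 14,988 and Alinity specificity is 14,977/14,988 = 99.927%. If the seroconverters are counted as positive, as III.F says, 15,000 − 14,988 − 12 = 0, which is correct. Subtraction gives a false 2 only if they are left out of the positives.

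**3. What a donor sensitivity would be worth**

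If the 2 donors were infected, A/(A+D) would be 10/12 = 83.3% (exact 95% interval 51.6% to 97.9%) for Alinity and 12/12 (73.5% to 100%) for PRISM. The intervals overlap widely. The documents give no donor prevalence. At an assumed 0.01% to 0.2%, 15,000 donors would include about 2 to 30 infected. With none missed, the exact lower limit is 0.025^(1/n): 15.8% for n = 2 and 88.4% for n = 30.

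**The case for a change.** The strongest contrary argument is that the plan gathers the evidence on missed donors and then names no summary for it. Supplemental testing, NAT and follow-up all serve to settle donor status, and the objective concerns donor screening. One line among some 15,000 per assay is not a summary. The disagreement cell of the agreement table mixes infected with uninfected donors. A donor found only through the Alinity gray zone, with PRISM nonreactive, does not even count as a disagreement. Naming the table in advance would also keep its appearance from depending on the results, at the cost of one small table per assay.

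The facts in this argument stand: no named summary gives the donor count in cell D, for either assay. The inference that the plan needs amending does not follow. The table must be filled for donors to obtain C and F, and doing so classifies the D donors as well. Section IX.A promises tables and listings without enumerating them, so silence in the text does not show that the count will be withheld. What the argument supports is a descriptive count with a few case histories. It does not support a further accuracy estimate. Supplemental testing depends on a reactive or gray zone result, follow-up is triggered by Alinity results only, and how NAT enters final status is left to separate algorithms that are not part of these documents. A donor sensitivity from such data could easily be overread.

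**Conclusion.** No change to the plan follows. The observation about the named summaries is correct, but cell D is properly absent from specificity, and estimating sensitivity in preselected, increased-risk and endemic specimens is a stated and sensible choice when donors are presumed to have almost no infection. No planned estimate is biased. The donors in question are classified, followed up and listed, so an analyst preparing the report can give the count without new data or new rules.

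In the assumed example, two missed donors leave Alinity specificity at 99.913%, and a donor sensitivity would carry an interval from 51.6% to 97.9%. These figures rest on invented counts and an assumed prevalence. The conclusion does not depend on them; it rests on the definitions of the measures and on what sections III.F, IX.A and IX.B.2.b already require. Showing the A to F counts for donors on both assays, with a short description of any cell D case and any index result removed under III.F, would be a useful but optional addition to the report.

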C. General Schedule of Events

Each site will configure and calibrate the Alinity s blood screening assays on the Alinity s System.

Prior to the start of protocol directed testing, the study staff will be trained in the operation of the Alinity s System. This training may occur at an Abbott facility or at the clinical site. The training will involve an overview of the system operation including system configuration, system maintenance, system calibration, control and specimen testing procedures. If needed, the clinical sites may supply leftover de-identified residual samples for the purpose of training or to confirm Alinity s System readiness. Documentation of study staff training will be maintained in the clinical study files.

Testing personnel will be required to demonstrate acceptable performance with each investigational assay prior to beginning system reproducibility or specimen testing for that assay. The Abbott monitor will provide the samples for this testing. This testing is used for training and to confirm the site's ability to perform the assay.

After successful completion of training, testing personnel will perform reproducibility and specimen testing using the Alinity s blood screening assay, calibrator and assay control clinical brochures and the procedures as described in this protocol.

Case report forms (CRF) will be utilized to document completion of the test procedures. The Abbott monitor will review the data and CRF to assure compliance to the study-directed procedures and to monitor the progress of the study.

The study will take approximately 5-10 months to complete.

D. Comparator Method

Each donor specimen and each specimen provided by Abbott will be tested with a designated FDA-licensed assay using the ABBOTT PRISM system, with the exception of specimens that are well characterized or have limited sample volume. This includes the following:

- HIV-1 Antigen positive - characterized by HIV-1 p24 testing.
- HIV-1 viral isolate - characterized by PCR amplification, DNA sequence, and phylogenetic analysis.
- Preselected *T. cruzi* Parasite Positive - characterized parasite positive by

Confidential Information

This material is the property of Abbott Laboratories and must not be disclosed or used, except as authorized in writing by Abbott Laboratories.

xenodiagnosis, hemoculture, or blood smear.

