- Subset of preselected *T. cruzi* serology positive and Chagas endemic specimens with limited sample volume that have comparator and supplemental testing data from a previous clinical study. If any discrepant ABBOTT PRISM Chagas results occurs between new results and the previous clinical study results, all of the archived specimens in these 2 categories will be tested with the ABBOTT PRISM Chagas assay.

The Abbott monitor will provide specific details of which specimens do not require comparator testing. All comparator testing will be performed according to the manufacturer's instructions and will include retesting, where required.

The comparator assay results will be compared to the corresponding results of the investigational assay.

E. Supplemental Testing

HIV, HBV and HCV nucleic acid testing (NAT) results for each of the donor specimens will be provided to Abbott to further characterize the donor specimens.

Specimens from donors, individuals at increased risk, individuals from endemic areas, Recovered HBV Individuals (for HBsAg assay) and individuals with HTLV-I/II associated diseases that are repeatedly reactive by either the Alinity s investigational assay or the comparator method or repeatedly gray zone negative (≥ 0.80 S/CO to < 1.00 S/CO) by the Alinity s investigational assay will be further tested using FDA licensed assays or research use only methods. This supplemental testing will be performed at the clinical sites or at external reference laboratories. Results obtained from this testing will be used to better characterize the specimen and assess final status.

The detailed algorithms for supplemental testing will be provided in a separate document for use with the clinical study protocol. Supplemental testing will be performed per each assay algorithm and if a specific assay is no longer commercially available or changes occur in the donor center's routine procedure, a revised version of the algorithm will be provided by the clinical monitor. Additional testing may be performed based on the clinical site's internal supplemental testing procedures. Data generated will be provided to Abbott and will be used for informational purposes.

Preselected positive specimens for each assay will have documented positive results prior to testing at the clinical sites. Supplemental testing is not required, but may be requested by the monitor for troubleshooting purposes.

Confidential Information

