Sensitivity can be also calculated as the proportion of repeatedly reactive (RR) specimens with positive status from specimens with positive status and nonreactive (NR) specimens with indeterminate status:

$$\text{Sensitivity} = A / (A + D + E) \times 100\%$$

A two-sided 95% confidence interval for overall sensitivity will be calculated using the exact method based on the binomial distributions.

All sensitivity calculations described above will also be done for the comparator assay.

d. Sample Size

Sample size for specificity is maximum of 15,000 and calculated based on the minimum power of 80% and $\alpha \leq 0.05$.

Sample size for sensitivity is not determined using statistical power calculations. Sample size is determined by the number of available specimens.

e. Level of Significance/Confidence Statement

Two-sided 95% confidence interval (CI) will be provided.

Confidential Information

This material is the property of Abbott Laboratories and must not be disclosed or used, except as authorized in writing by Abbott Laboratories.

f. Data Handling Convention

All results from this testing that are performed according to the protocol and not excluded will be eligible for analysis. Reasons for any exclusion will be captured in the database.

X. Conduct of the Study

A. Responsibilities for Conduct of the Study

- 1) The investigator will have written and dated approval/favorable opinion from the [Institutional Review Board (IRB) or Independent Ethics Committee (IEC)] for the protocol and other documents as specified by the [IRB/IEC] before initiating the study. In some cases, the [IRB/IEC] may provide an expedited or exception review.
- 2) The investigator is responsible for reporting to the [IRB/IEC] and obtaining the necessary approvals from his/her site administration.
- 3) Abbott Laboratories will not initiate the study until the required pre-study documents are received from the site. Pre-study documents are aligned with GCP requirements and a detailed listing of the required pre-study documents will be provided to the investigator by the Abbott monitor.
- 4) The investigator will perform the study in accordance with GCP. The Abbott monitor will provide the investigator with the GCP-aligned list of investigator requirements.
- 5) The Abbott monitor will provide the investigator with the Guidance for Industry Investigator Responsibilities – Protecting the Rights, Safety, and Welfare of Study Subjects (October 2009) for reference.

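### For HIV Ag/Ab Combo and Chagas, the planned overall sensitivities of Alinity s and PRISM rest on different specimens, and each pools positives established under two different reference standards

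*Combined protocol and SAP*

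**What the plan says.** Section IX.B.2.a defines the pool: "the sensitivity will be calculated using results from preselected positive populations and from endemic or increased risk populations". Section IX.B.2.c lists the same populations ("The evaluation of sensitivity will include results of the following specimens: preselected positive, individuals at increased risk of infection", and/or endemic-area individuals) and defines sensitivity as A/(A+D), with A/(A+D+E) as an option. The one interval it specifies is this: "A two-sided 95% confidence interval for overall sensitivity will be calculated using the exact method based on the binomial distributions". It then adds: "All sensitivity calculations described above will also be done for the comparator assay". Section IX.B.2.e promises intervals in general terms: "Two-sided 95% confidence interval (CI) will be provided".

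Section III.D has specimens tested on PRISM "with the exception of specimens that are well characterized or have limited sample volume". The listed exemptions are:
- "HIV-1 Antigen positive - characterized by HIV-1 p24 testing"
- HIV-1 viral isolates
- T. cruzi parasite positives
- a limited-volume subset of T. cruzi serology-positive and Chagas endemic specimens that already has comparator and supplemental data from a previous study.

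The section adds: "The Abbott monitor will provide specific details of which specimens do not require comparator testing".

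Under section III.E, preselected positives have documented positive results before testing. Increased-risk and endemic specimens go to supplemental testing if they are repeatedly reactive on either assay or repeatedly gray zone on Alinity s. Under section VI.C.2, step 5, an initial Alinity s S/CO below 0.80 needs no further testing.

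**The concern.** Section II promises a comparison with licensed assays, so readers will set the two overall sensitivities side by side. Nothing in section IX.B.2.c restricts them to specimens run on both assays. For HIV Ag/Ab Combo and Chagas, part of any difference could come only from specimens that PRISM never tested.

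The second issue is the reference standard. A preselected positive counts whatever the two assays show. An increased-risk or endemic positive that both assays miss, with Alinity s below 0.80 S/CO, gets no in-study work-up. Unless prior supplemental data exist, it generally does not reach cell D. That part of the pool is conditional on the assays being evaluated, but it would be reported as plain sensitivity.

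**Working it through.** **Stated figures.** The plan gives no sensitivity target, expected value or power. Its one relevant total is about 7,600 sponsor-provided specimens. The table in VI.A.1 gives HIV 2,350 + HTLV 1,700 + HBsAg 850 + anti-HBc 800 + anti-HCV 800 + Chagas 900 = 7,400, within 3% of that total.

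**Preselected specimens available to each assay (VI.A.1 less the III.D exemptions).**
- HIV, Alinity s: 1,000 + 200 + 50 = 1,250. PRISM: 1,250 − 50 = 1,200 (4.0% fewer).
- Chagas, Alinity s: 100 + 200 = 300. PRISM: 300 − 100 = 200 (33.3% fewer). This counts archived PRISM results for the limited-volume subset; if they do not count, the PRISM figure is smaller.

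**Overall denominators.** Let R be the positives among increased-risk/endemic specimens. The documents give no positivity, so 2% to 20% is assumed. Chagas: R = 12 or 120 of 600. HIV: R = 22 or 220 of 1,100.

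**Different specimens, exact (Clopper-Pearson) 95% intervals.** Miss counts are assumptions.

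| Scenario | Alinity s | PRISM |
|---|---|---|
| Chagas 2%, 5 exempt misses only | 307/312 = 98.40% (96.30–99.48) | 212/212 = 100% (98.28–100) |
| Chagas 20%, 5 exempt misses only | 415/420 = 98.81% (97.24–99.61) | 320/320 = 100% (98.85–100) |
| HIV 2%, 5 exempt misses only | 1267/1272 = 99.61% (99.09–99.87) | 1222/1222 = 100% (99.70–100) |
| HIV 20%, 5 exempt misses only | 1465/1470 = 99.66% (99.21–99.89) | 1420/1420 = 100% (99.74–100) |
| Chagas 2%, 2 shared misses among serology positives, no exempt miss | 310/312 = 99.36% | 210/212 = 99.06% |

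In the first scenario the gap is 1.60 points against Alinity s. In the last it is 0.30 points in its favour. Restricted to the 212 common Chagas specimens, both gaps vanish: 212/212 against 212/212, and 210/212 against 210/212. Each missed exempt specimen moves the Alinity s figure by 1/420 to 1/312 = 0.24 to 0.32 points for Chagas and 1/1470 to 1/1272 = 0.07 to 0.08 points for HIV. The five HIV misses, shown within their own category, read 45/50 = 90.0% (78.2–96.7).

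**Work-up dependence.** Assume true sensitivity s = 0.98 for both assays, no gray-zone rescue and no prior supplemental data. Let q be the probability that both assays miss: 0.02² = 0.0004 if independent, 0.01 if half of the misses are shared, 0.02 if all are.
- Increased-risk/endemic component: s/(1−q) = 98.04%, 98.99% and 100%.
- Pooled figure, with P preselected positives: bias = s(P+R)/(P+R(1−q)) − s.

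| Assay | P | R | Independent | Half shared | All shared |
|---|---|---|---|---|---|
| HIV | 1,250 | 22 / 220 | 0.001 / 0.006 | 0.017 / 0.147 | 0.034 / 0.294 |
| HTLV | 600 | 20 / 200 | 0.001 / 0.010 | 0.032 / 0.246 | 0.063 / 0.492 |
| Chagas | 300 | 12 / 120 | 0.002 / 0.011 | 0.038 / 0.281 | 0.075 / 0.563 |
| HBsAg, anti-HBc, anti-HCV (each) | 400 | 8 / 80 | 0.001 / 0.007 | 0.019 / 0.164 | 0.038 / 0.328 |

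Entries are percentage points, at 2% / 20% positivity. The largest (Chagas, 20%, all shared) falls to 0.284 at s = 0.99 and 0.142 at s = 0.995.

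**The case against.** The strongest reply is that no decision rule is shown to be affected. Sensitivity is not powered, no margin or acceptance criterion against PRISM is stated, and percent agreement is already a paired comparison. The five-miss scenario is arbitrary, and its Chagas intervals overlap. All of this is true. But percent agreement is not sensitivity, and the plan commits to computing both sensitivities in support of the comparison in section II. A like-for-like basis is a fair requirement.

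On work-up, final status follows algorithms held in a separate document, and section VI.A.1 says supplemental results are documented as applicable. Prior data may therefore bring some jointly missed positives into cell D. That limits the second issue to separate reporting and disclosure.

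A reader might also infer that category results are ruled out. They are not: section IX.B.2.b names specimen category as an analysis variable, and section IX.B.2.e promises intervals. The text simply does not say that sensitivity is reported that way. The absence of category rows alone would be a request for detail.

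**Conclusion.** The point holds for the matched comparison and for the split by reference standard, and the plan should be changed. The specimen mismatch follows directly from sections III.D, VI.A.1 and IX.B.2.c. Its effect depends on assumed misses and positivity, and on archived PRISM Chagas results being counted.

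The documents do not support three stronger readings.
- **That the mismatch works in one direction.** The Chagas scenarios show it can favour either assay.
- **That only HIV and Chagas can be affected.** The listed exemptions concern those two, but the list is not shown to be closed and the monitor supplies the details. Under A/(A+D+E), cell E is specific to the assay scored, so denominators could differ for any assay with indeterminate results.
- **That overall sensitivity is materially inflated by the work-up trigger.** At 98% true sensitivity the pooled bias is about 0.01 points or less with independent misses. It reaches about 0.56 only with every miss shared, 20% positivity and no gray-zone rescue or prior data. The increased-risk/endemic component is more exposed, which is why it should be shown separately.

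**What to change.** In section IX.B.2.c:
1. State that Alinity s and PRISM sensitivities are compared on specimens with results from both assays.
2. Say whether archived PRISM Chagas results count as PRISM results.
3. Show PRISM-exempt specimens for Alinity s alone, outside the comparison.
4. Report exact 95% intervals separately for preselected positives and for increased-risk/endemic specimens. Keep to the populations that this section already lists, so that Recovered HBV (50) and HTLV-associated disease (100) specimens are not drawn into sensitivity by the change.
5. Label the increased-risk/endemic result as conditional on work-up triggered by repeat reactivity on either assay or an Alinity s gray-zone result, or on prior supplemental data.

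The cost is wording and a few table rows, with no new testing. Intervals are wider in small groups: 50/50 has a lower limit of 92.9% and 100/100 one of 96.4%. The label discloses the work-up dependence but does not remove it.
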